6.4 Randomisation criterion

1. Have kept a food diary for at least 5 days (minimum one entry per day) in the period between screening and randomisation

To be randomised, the above randomisation criterion must be answered “yes”.

6.5 Criteria for premature discontinuation of trial product

Efforts must be made so that subjects attend and complete all scheduled visit procedures. Subjects should stay in the trial regardless of adherence to randomised treatment, adherence to visit schedule or missing assessments. Only subjects who decline any further contact with the site in relation to the trial or withdraw consent are considered as withdrawn from the trial (see Section [6.6](#)).

The subject may be prematurely discontinued from trial product at the discretion of the investigator due to a safety concern.

The subject must be prematurely discontinued from trial product if the following applies:

1. Included in the trial in violation of any of the inclusion and/or exclusion criteria and/or randomisation criterion
2. Safety concern (not covered by any of below criteria) or unacceptable intolerability to trial product, as judged by the investigator
3. Hypersensitivity to trial product(s). If a hypersensitivity reaction occurs, discontinue trial product and other suspect medications
4. More than one episode of severe hypoglycaemia, or repeated episodes of documented symptomatic hypoglycaemia (ADA classification), despite lowering of insulin dose (as judged by investigator)
5. Pregnancy
6. Intention of becoming pregnant
7. Suspicion of pancreatitis (see Section [8.4.3.2](#) and [8.8.1](#))
8. Suspicion of acute gallstone disease (see Section [8.4.3.2](#) and [8.8.2](#))
9. Suspicion of drug-induced liver injury (DILI) (see Section [8.4.3.2](#) and [8.8.4](#))
10. Calcitonin ≥ 100 ng/L
11. Psychiatric disorder(s) that cannot be adequately treated with psycho- and/or pharmacotherapy (see Section [8.4.3.2](#), [8.6.5](#) and [8.8.5](#))
12. Initiation of anti-obesity medication and/or (plans for) weight loss surgery
13. Initiation of treatment with GLP-1 receptor agonist or DPP-IV inhibitors

14. Simultaneous participation in another clinical trial of an approved or non-approved investigational medicinal product

See Section [8.1](#) for procedures to be performed for subjects discontinuing trial product prematurely.

It is allowed for subjects meeting the premature discontinuation criteria or who have wished to discontinue prematurely to be restarted on the trial product should the suspicion not be confirmed or if the condition has been resolved at the investigator's discretion. Trial product may be restarted for subjects meeting discontinuation criteria 8 should the gallbladder be removed.

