5.3 Treatment of subjects

5.3.1 Investigational medicinal product

The investigational medicinal product (IMP) is injected subcutaneously (s.c.) once daily for 56 weeks. Dose escalation of trial product will take place during the first 4 weeks after randomisation (see [Table 5-1](#)).

Table 5-1 Dose escalation and treatment period

IMP	Dose	Duration
Liraglutide/placebo	0.6 mg	1 week
Liraglutide/placebo	1.2 mg	1 week
Liraglutide/placebo	1.8 mg	1 week
Liraglutide/placebo	2.4 mg	1 week
Liraglutide/placebo	3.0 mg	52 weeks
Follow up period	0 mg	4 weeks

If the subject does not tolerate an increased dose during the dose escalation window, the investigator can delay the dose escalation by maintaining the subject at the current dosage step for one additional week. Such a delay is allowed only once during dose escalation (i.e. maximum allowed time for complete dose escalation to 3.0 mg is 5 weeks). After reaching the maintenance dose (3.0 mg), the dose and dosing frequency should not be changed.

If a single dose is missed, the once-daily regimen should be resumed as prescribed at the next scheduled dose. If more than 3 consecutive days have elapsed since the last dose, subject should re-initiate dose escalation, (e.g. restart the dosing at 0.6 mg and follow the dose escalation schedule again). This is done to reduce the occurrence of gastrointestinal symptoms associated with re-initiation of treatment.

NB: Additional or increased dose should not be taken to make up for missed doses.

Trial product can be taken at any time of day, irrespective of timing of meals. Trial product can be injected s.c. in the abdomen, thigh, or upper arm. The injection site and timing can be changed without dose adjustment.

NB: Trial product must not be administered intravenously or intramuscularly.

If a subject cannot tolerate the 3.0 mg dose, or if any of the other treatment discontinuation criteria are met, then treatment with trial product must be discontinued. For treatment discontinuation reasons, please refer to Section [6.5](#). In case this happens, it is acceptable to restart trial product (at the discretion of investigator and according to the local clinical practice); the dose must be escalated according to the algorithm above, and date of restart and rationale must be documented in the CRF.

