5.4 Treatment after discontinuation of trial product

When discontinuing trial products, the subject may be switched to a suitable marketed product at the discretion of the investigator.

After premature discontinuation of trial product (temporary/permanent), the subject should still remain in the trial and follow the IBT sessions and site visits if possible, see Section [8.1](#). In this case, the investigator must note down the current treatment in the medical record and eCRF. If the subject has re-started the trial product, the investigator must note down details in the medical record and eCRF, see Section [5.3.1](#).

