If a subject meets a discontinuation criterion, the trial product must be immediately discontinued and the date should be noted in the medical records and eCRF. Discontinuation can be either temporary or permanent. The last paragraph of Section [6.5](#) outlines which discontinuation can be considered temporary. The investigator must also note down the date in the medical record and eCRF once there is resolution and the subject has re-started the trial product.

The subject may also wish to discontinue trial product temporarily or permanently, irrespective meeting any criteria. Discontinuation of treatment with trial product, whether temporary or permanent, must not prompt the investigator to withdraw the subject from the trial. Instead, the subject should maintain adherence to trial visits and procedures to the extent possible.

In cases where the subject is not willing to attend all scheduled visits after discontinuation of trial product, efforts must be made to collect as much of the scheduled data as possible. Especially important is collection of the data points (primarily) at visit 24 (week 56). Statistical considerations emphasizing the importance can be found in Section [17](#).

Premature trial product discontinuation should be registered in the eCRF and in IWRS. The trial product can be interrupted by performing a 'treatment status' session in IWRS, to indicate subject should no longer receive trial product. The primary reason for discontinuation of trial product must be specified when recording the treatment discontinuation in the eCRF. If the discontinuation of trial product is judged permanent or of a longer period, drug accountability until discontinuation must be performed in IWRS.

If the subject has previously discontinued trial product, it is possible, at the discretion of the investigator and at the wish of the subject, to re-initiate treatment with trial product. This will only apply if it can be confirmed that the subject has not withdrawn consent, does not fulfil any of the criteria, leading to permanent discontinuation or if a criterion leading to temporary discontinuation has been resolved. A 'treatment status' session is performed in the IWRS, to indicate that the subject should again receive trial product. See Section [10](#) for registration in IWRS. This should be further noted in the medical records and eCRF.

Withdrawal from trial

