In case of suspicion of drug-induced liver injury (DILI), following additional information should be reported if available on the drug induced liver injury form:

- Signs and symptoms of drug induced liver injury
- Specific laboratory test supporting a diagnosis of drug induced liver injury (see Section [8.8.4](#))
- Treatment given for the event
- Relevant risk factors associated with the event

Prompt testing (at central laboratory) including alanine aminotransaminase (ALT), aspartate aminotransferase (AST), alkaline phosphatase (ALP), international normalised ratio (INR) and total bilirubin (TBL) should be done and trial product should be discontinued until the abnormalities return to normal or baseline state.

Additional clinical information such as related symptoms, risk factors and contributing conditions (e.g., viral hepatitis, autoimmune hepatitis, alcoholic hepatitis, hepatobiliary or pancreatic disorders) should be gathered to seek a possible cause of the observed laboratory test abnormalities.

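### The general restart rules in 5.3.1 and 6.5 make no exception for confirmed pancreatitis, against 8.8.1 and 18.1, nor, in a softer conflict with 8.8.4, for confirmed drug-induced liver injury

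*Protocol*

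**What the plan says.** **General restart rules (Protocol).** Section 5.3.1 sets its scope with "If a subject cannot tolerate the 3.0 mg dose, or if any of the other treatment discontinuation criteria are met": product must then be stopped. It continues: "In case this happens, it is acceptable to restart trial product (at the discretion of investigator and according to the local clinical practice"), subject to a new dose escalation and documentation of the restart. Section 5.4 sends restarts back to 5.3.1 and asks only for a record: "If the subject has re-started the trial product, the investigator must note down details in the medical record and eCRF".

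The last paragraph of 6.5 covers subjects who met a discontinuation criterion or who chose to stop. At the investigator's discretion, they may be "restarted on the trial product should the suspicion not be confirmed or if the condition has been resolved". Its one criterion-specific sentence adds a permission: restart under criterion 8 (gallstone disease) after gallbladder removal.

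**Limits on restart.** Section 8.1 allows re-initiation if the subject "does not fulfil any of the criteria, leading to permanent discontinuation or if a criterion leading to temporary discontinuation has been resolved". The same section says that the last paragraph of 6.5 "outlines which discontinuation can be considered temporary". Section 10 allows re-initiation in the IWRS only when no discontinuation criterion is met, and refers to 8.1.

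**Event-specific rules.** Section 8.8.1 makes confirmed acute pancreatitis a permanent stop, worded as *must*, and foresees re-initiation only if pancreatitis is ruled out. Section 18.1 says that liraglutide should not be started again after confirmed pancreatitis. Section 8.8.4 words the permanent stop for confirmed DILI as *should*, and foresees re-initiation only if the diagnosis is not supported. Section 8.4.3.2, on suspected DILI, says "trial product should be discontinued until the abnormalities return to normal or baseline state".

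Amendments 1 to 3 leave all of these provisions unchanged.

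**The concern.** On their plain words, the general rules reach further than the event-specific ones. In 6.5, resolution of the condition is an alternative to the suspicion not being confirmed, so it can cover a confirmed event that has since healed. Section 5.3.1 does not ask even for that: it names only the investigator's discretion and local practice.

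What is at stake is re-exposure after an event that the protocol's own safety sections treat as a permanent stop. For DILI, laboratory values that normalise once the drug is withdrawn do not show that the drug was not the cause. Two sites could also handle the same confirmed event differently, depending on which section they open. Section 19.2 mentions re-initiation among the measures against missing data, so the general rules are likely to be consulted.

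**Working it through.** No arithmetic applies, and the plan states no figure on this point. The check is a comparison of the provisions.

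| Protocol section | Applies to | Restart allowed when | Rule once the event is confirmed |
|---|---|---|---|
| 5.3.1 | any discontinuation criterion | investigator's discretion and local practice | none stated |
| 6.5, last paragraph | any criterion, or subject's choice | suspicion not confirmed, or condition resolved; criterion 8 also after gallbladder removal | none stated |
| 8.8.1 | acute pancreatitis | ruled out | permanent stop (*must*) |
| 18.1 | pancreatitis | not addressed | no restart (*should not*) |
| 8.8.4 | DILI | diagnosis not supported | permanent stop (*should*) |
| 8.8.2 | acute gallstone disease | cholelithiasis ruled out, or gallbladder removed | permanent stop (*must*), subject to those two exceptions |

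1. **Pancreatitis (criterion 7).** Section 8.8.1 has one restart route. Section 6.5 has that route in substance plus a second, resolution. Section 5.3.1 has no condition tied to the event. A confirmed case that has healed is barred by 8.8.1 and 18.1 but not by the words of 5.3.1 or 6.5. This is a firm conflict.

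2. **DILI (criterion 9).** The structure is the same, but 8.8.4 uses *should*, so the discretionary rules collide with a strong recommendation and not with an absolute bar. Criterion 9, "Suspicion of drug-induced liver injury (DILI"), cites both 8.4.3.2 and 8.8.4. The first describes a stop lasting until the values normalise and does not separate confirmed from unconfirmed injury. The second makes the stop permanent on confirmation. A site that follows both links finds two different end-points.

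3. **Gallstone disease (criterion 8).** Sections 6.5 and 8.8.2 both name gallbladder removal, and a suspicion that is not confirmed corresponds closely to cholelithiasis being ruled out. The two sections largely agree. A cross-reference is enough.

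4. **Does 8.1 settle it?** It bars restart where a criterion leads to permanent discontinuation, but it lists no such criteria. For what is temporary it points to the last paragraph of 6.5, which marks nothing as permanent. The reader has to bring in 8.8.1 and 8.8.4 to close the gap.

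5. **Does Section 10 settle it?** It requires that no discontinuation criterion is met. Criteria 7 and 9 are worded as suspicions, so a site could regard them as no longer met once the event is over. Section 10 otherwise relies on 8.1.

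6. **Count.** Of the 14 criteria in 6.5, one is in firm conflict (7), one in softer conflict (9) and one largely reconciled (8).

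**The case against.** The strongest reply is that the sections, read together, already bar the restart. Only criteria 7, 8 and 9 in 6.5 are framed as suspicions, so the route for an unconfirmed suspicion naturally belongs to them, and the resolution route to other criteria such as intolerability or pregnancy. The gallbladder sentence supports this: it would add little if any healed, confirmed event already qualified. Section 8.1 cites 6.5 only for what may be temporary. Permanence is stated in 8.8.1 and 8.8.4, which criteria 7 and 9 cite directly. Section 5.3.1 refers to 6.5 for discontinuation reasons, 6.5 refers to 8.1 for procedures, and Section 10 also points to 8.1. A site that used 5.3.1 alone would be ignoring an explicit *must*.

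Much of this stands. The combined reading is plausible and probably what was intended. But 6.5 does not say that its two routes apply to different criteria, no precedence between general and specific rules is stated in these sections, and the restart sentence in 5.3.1 stays unqualified on any reading.

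Three stronger inferences should be resisted:

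- A reader might take the definition of a resolved adverse event in 12.1.1 as proof that 6.5 covers healed confirmed events. That definition serves the coding of event outcomes, and nothing links it to 6.5.
- A reader might take 8.4.3.2 as ordering a restart once liver values normalise. It describes when the stop ends for suspected injury and does not order a restart.
- A reader might place DILI and gallstone disease on the same footing as pancreatitis. The wording in 8.8.4 is softer, and 6.5 and 8.8.2 largely agree.

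**Conclusion.** The inconsistency is real and should be corrected. It is firm for confirmed pancreatitis, softer for confirmed DILI and nearly absent for gallstone disease. It concerns consistency of wording on a subject-safety matter, not a flaw in the design.

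A reader might infer that the protocol as a whole permits re-exposure after these events. The documents do not support that: 8.1, 8.8 and 10 can be combined into a bar. What they support is narrower. Two general provisions, taken as written, permit what the safety sections rule out or advise against, and the link meant to reconcile them leads back to one of those provisions.

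Few subjects are likely to be affected; 18.1 reports few pancreatitis events in the weight-management trials. The documents give no rate for confirmed pancreatitis or DILI, and no basis for judging how often an investigator would restart against 8.8, so the number of wrongful restarts cannot be estimated. Power and alpha do not change. The conclusion rests only on the wording of the current text.

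**What to change.** Add to the restart text in 5.3.1 and to the last paragraph of 6.5: *Trial product must not be restarted after confirmed pancreatitis or confirmed DILI (see 8.8.1, 8.8.4); for confirmed gallstone disease see 8.8.2.* Because 8.1 already points to that paragraph of 6.5, and 5.4 to 5.3.1, the exception then reaches those sections too.

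In 8.4.3.2, state that restart after the values have normalised applies only if the diagnosis of DILI is not supported.

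Optional: change *should* to *must* for the permanent stop in 8.8.4, to align it with 8.8.1. This is a wording preference and the point does not depend on it.

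The cost is a protocol amendment with one sentence in two places and one clause in a third. It needs no extra data, visits or subjects, and no change to the statistical analysis.

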8.8.4 Hepatic event (suspicion of drug-induced liver injury)

Please consider discontinuing trial product if :

- 1) ALT or AST >5xUNL, or

2) ALT or AST > 3x UNL and (total bilirubin >2xUNL or INR >1.5), or

3) ALT or AST >3xUNL with the appearance of fatigue, nausea, vomiting, right upper quadrant pain or tenderness, fever, rash, and/or eosinophilia (>5%).

For the above events, prompt repeat testing at central laboratory, of ALT, AST, ALP, INR and total bilirubin should be done. Thereafter, repeat testing (at central laboratory) of ALT, AST, ALP, INR and total bilirubin should be done regularly until the abnormalities return to normal or baseline state. Additional clinical information such as related symptoms, risk factors and contributing conditions (e.g. viral hepatitis, autoimmune hepatitis, alcoholic hepatitis, hepatobiliary or pancreatic disorders) should be gathered to seek a possible cause of the observed laboratory test abnormalities. Although the trial product is discontinued, no 'treatment status' session should be made in IWRS and the subject should remain in the trial.

In case of suspicion of DILI, the trial product must promptly be discontinued (no 'treatment status' session should be made in IWRS before a diagnosis is confirmed).

The event must be reported as an AE requiring additional data collection (see Section [8.4.3.2](#) and Section [12](#)).

If DILI is confirmed, the subject should permanently discontinue the trial product. Appropriate treatment and careful monitoring of the subject should be initiated. Furthermore, the subject should be encouraged to remain in the trial (see Section [8.1](#)).

Trial product can be re-initiated at the investigator's discretion if diagnosis of DILI is not supported.

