9.5 Auxiliary supplies

Auxiliary supplies comprise supplies other than trial products. The following auxiliary supplies will be provided by Novo Nordisk in accordance with the TMM:

- Needles for pre-filled pen (maximum length to be used is 8 mm)
- Directions for use for pre-filled pen
- Blood glucose (BG) meter
- BG auxiliaries including test strips, lancets, instructions and control solution.

Only needles provided by Novo Nordisk must be used for administration of trial product.

10 Interactive web response system

A trial-specific interactive web response system (IWRS) will be set up which can be accessed at any time via the internet or telephone. Access to the IWRS must be restricted to and controlled by authorised persons.

IWRS is used for:

- Screening
- Screening failure
- Randomisation
- Medication arrival
- Dispensing
- Treatment status
- Code break
- Drug accountability
- Data change

IWRS user manuals will be provided to each trial site.

Premature treatment discontinuation and re-initiation

If the investigator or the subject has decided to discontinue treatment, but the subject has not withdrawn consent, it is possible to re-initiate treatment, if no discontinuation criteria are met (see Section [8.1](#)). The subject will remain in the same treatment arm, and a new dose escalation period will be started, if the subject resumes treatment. The investigator must make a note and record dates of any discontinuation and re-initiation dates in the medical records and eCRF.

To register discontinuation of trial product (temporary or permanent), a 'treatment status' session is performed in the IWRS, to indicate subject should no longer receive trial product. Similarly, if the treatment should later be re-initiated, a 'treatment status' session is performed in the IWRS, to indicate subject should again receive trial product.

Withdrawal

In the case subject has withdrawn consent, a 'treatment status' session must be performed in IWRS, to indicate that subject should no longer receive trial product. If possible after confirmation by the monitor, the subject will be registered as 'withdrawal', to ensure that subject is not allowed to re-initiate trial product.

If the subject is temporarily lost to follow up during the trial, the IWRS session should not be completed until the scheduled Visit 24 at week 56 to confirm the final status.

11 Randomisation procedure and breaking of blinded codes

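### The restart permissions in Protocol 6.5 and 5.3.1 do not exclude the confirmed diagnoses that Section 8.8 makes a permanent stop

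*Protocol*

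**What the plan says.** Protocol 6.5 lists the criteria for mandatory discontinuation of trial product. Criteria 7, 8 and 9 are suspicion of pancreatitis, of acute gallstone disease and of DILI. Each refers to 8.4.3.2 and to its own part of 8.8. The last paragraph of 6.5 then allows restart for subjects who met the criteria, at the investigator's discretion, "should the suspicion not be confirmed or if the condition has been resolved". Its only criterion-specific sentence concerns criterion 8, where restart is allowed once the gallbladder is removed.

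Protocol 5.3.1 requires a stop when any discontinuation criterion is met, refers to 6.5 for the reasons, and goes on: "it is acceptable to restart trial product (at the discretion of investigator and according to the local clinical practice").

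Protocol 8.8 is stricter once a diagnosis is confirmed:

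- 8.8.4: "If DILI is confirmed, the subject should permanently discontinue the trial product". Re-initiation is left to the investigator's "discretion if diagnosis of DILI is not supported".
- 8.8.1: confirmed acute pancreatitis is a permanent stop. Restart is mentioned only if the diagnosis is ruled out.
- 8.8.2: confirmed acute gallstone disease is a permanent stop, unless cholelithiasis is ruled out or the gallbladder has been removed.

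Two general limits apply elsewhere. Under 8.1, a subject may restart only if he or she "does not fulfil any of the criteria, leading to permanent discontinuation", or if a criterion behind a temporary stop has resolved. Section 10 says "it is possible to re-initiate treatment, if no discontinuation criteria are met".

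**The concern.** The ground in 6.5 that the condition has resolved is an alternative to the ground that the suspicion was not confirmed, and it is tied to no particular criterion. On its words it covers a confirmed case that has since settled. An investigator who looks up restart in 6.5 or 5.3.1 therefore finds a permission where 8.8 has a prohibition.

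What is at stake is subject safety: re-exposure after confirmed liver injury or pancreatitis, or with gallstone disease still present, is what 8.8 is there to prevent.

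**Working it through.** No arithmetic applies. The check takes a subject who met criterion 7, 8 or 9 and asks what each section says about restart.

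| Subject's situation | 6.5, last paragraph | 5.3.1 | 8.8 |
|---|---|---|---|
| Suspicion not confirmed | Allowed | Allowed | Allowed |
| Confirmed DILI, resolved | Allowed (resolved) | Allowed (discretion) | Not allowed (8.8.4) |
| Confirmed acute pancreatitis, resolved | Allowed (resolved) | Allowed (discretion) | Not allowed (8.8.1) |
| Confirmed gallstone disease, episode resolved, gallbladder in place, cholelithiasis not ruled out | Allowed (resolved) | Allowed (discretion) | Not allowed (8.8.2) |
| Confirmed gallstone disease, gallbladder removed | Allowed | Allowed | Allowed (8.8.2) |

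The first and last rows agree. The three middle rows conflict.

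The next question is whether other text settles those three rows.

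1. **8.1.** The bar on criteria that lead to permanent discontinuation would settle them if those criteria were identified. 8.1 does not list them, and the list in 6.5 labels none as permanent. A reader can take them from the word permanent in 8.8. But 8.1 also says that the last paragraph of 6.5 "outlines which discontinuation can be considered temporary", and that paragraph contains the resolved-condition ground. The safeguard therefore leads back to the sentence that needs limiting.
2. **Section 10.** Re-initiation requires that no discontinuation criterion is met. Criteria 7 to 9 are worded as suspicions, so after resolution an investigator could regard them as no longer met. Section 10 itself refers to 8.1. The registration that blocks re-initiation in the web response system is described only for withdrawn consent.
3. **18.1.** The benefit-risk section repeats the no-restart rule for confirmed pancreatitis. It has no hepatic entry, and its gallstone paragraph gives no restart rule. For DILI and gallstone disease the specific rule stands in 8.8 alone.
4. **Amendments 1 to 3.** The changes shown do not touch 5.3.1, 6.5, 8.1, 8.8 or Section 10.

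On the analysis side, the effectiveness estimand applies regardless of adherence. The primary imputation pools missing week 56 weights whether or not the subject was on treatment, and draws on all available placebo weights. Whether such a subject restarts does not change that method.

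**The case against.** The strongest reply is that a specific rule governs a general one, and that the protocol leads the reader to the specific rule. 5.3.1 points to 6.5, criteria 7 to 9 point to 8.8, and the line just before the restart paragraph in 6.5 points to 8.1. The specific event form for suspected DILI also brings the investigator to 8.8.4. Under 8.8.4 the treatment-status session waits for a confirmed diagnosis, so a confirmed case should be registered and restart should then need a further session under Section 10.

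There is also evidence of intent inside 6.5. Its gallbladder sentence would add little if the general sentence already reached confirmed disease. The two grounds can be paired with the criteria: an unconfirmed suspicion fits criteria 7 to 9, and a resolved condition fits states such as pregnancy or a psychiatric disorder. On that reading 6.5 and 8.8 agree.

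Much of this stands. A careful reader can reach the right action, and the sponsor's intention is clear from 8.8. The pairing is plausible, but the text does not state it: the sentence applies both grounds to any subject who met the criteria. The pointer from 8.1 back to 6.5 also weakens the chain that is supposed to correct it.

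A reader might infer that 8.4.3.2 is a further restart permission, since it says "trial product should be discontinued until the abnormalities return to normal or baseline state". It is not. That text concerns suspected DILI, sets a hold while the abnormality is followed, and grants no restart.

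**Conclusion.** The point holds as a literal conflict between the general restart text (6.5 and 5.3.1) and the rules for confirmed diagnoses (8.8.1, 8.8.2 and 8.8.4). It is worth correcting but minor. That few subjects would be affected is an assumption, because the documents give no rate for any of the three events. The primary analysis is unaffected.

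Two stronger readings go too far. One is that the protocol as a whole authorises re-exposure after confirmed DILI. It does not: 8.8.4 says the opposite, and 8.1 and Section 10 limit restart in general terms. The other is that the gap is peculiar to DILI. Confirmed pancreatitis has the same literal conflict, as does confirmed gallstone disease with the gallbladder in place and cholelithiasis not ruled out.

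The strength of the 8.8 rules also differs. 8.8.1 and 8.8.2 say must, while 8.8.4 says should, so the conflict for DILI is with a strong recommendation.

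**What to change.** 1. Add to the last paragraph of 6.5: *For criteria 7, 8 and 9, restart after a confirmed diagnosis is governed by Sections 8.8.1, 8.8.2 and 8.8.4: trial product should not be restarted after confirmed acute pancreatitis or confirmed DILI even if resolved, nor after confirmed gallstone disease unless cholelithiasis is ruled out or the gallbladder has been removed.*
2. In 5.3.1, make the restart sentence *subject to Sections 6.5 and 8.8*.
3. Optional: in 8.4.3.2, refer to 8.8.4 for restart. This is only a matter of wording.

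The 6.5 sentence uses should not, which keeps the wording of 8.8.4 and adds no stricter rule. It leaves the firmer wording of 8.8.1 and 8.8.2 in force through the cross-reference.

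The cost is one sentence and one clause in a protocol amendment. There are no new assessments and no change to the SAP or sample size. Section 25 requires approval before an amendment is implemented, so the edit is best carried with another amendment.
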